***Monthly CHOIR surveys:*** Patients will be assessed monthly for satisfaction with the study, current opioid use, hospital or emergency medical visits, depressive symptoms, suicidality, and other factors that may indicate symptom worsening and require follow-up. Suicidality will trigger e-alerts to the prescribing clinician, site director, site coordinator, study manager, and the overall principal investigator. Site-specific messages will provide patients with instructions for non-emergency triage (e.g., calling the clinic for telephone or in-person follow-up) and emergency triage options in their community (e.g., calling 911), rapid contact with clinic staff, and crisis hotlines.

Weekly and monthly surveys will ensure careful monitoring of patients, triage of issues, and close connections with study staff and prescribing providers to enable rapid taper adjustments and address any additional needs. Study clinicians may securely access EMPOWER CHOIR via a web browser to review patient responses and coordinate participant activities. Comprehensive patient-reported survey batteries will be administered at baseline and at six and 12 months, including data on opioid use.

***Randomization.*** Each site will conduct a site-specific randomized controlled trial using a randomized design, allowing rapid accrual of patient cohorts (N=8–18 per cohort) assigned to the same intervention arm and timely delivery of behavioral interventions. Patients entering the study will be automatically assigned to the currently open intervention arm. The ordering of intervention arms will remain blinded to patients and clinicians, who cannot choose or direct group assignment. Study coordinators, while unblinded, will be trained to maintain clinician and patient blinding. After enrollment and baseline measures, group assignments will be revealed to participants. A statistician unaffiliated with patient care will create unique randomization schemes for each site, enabling prompt receipt of behavioral interventions for those assigned to such arms (ideally within two to ten weeks of taper initiation). Behavioral intervention timing will be recorded.

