#### **Sample Size Calculations and Study Power**

The power calculation is primarily based on the study aims for comparative effectiveness. The original power calculation was for  $N = 850$ , with  $N = 750$  patients completing the month-12 survey. The study sample size was later reduced to  $N = 489$  participants completing the month-12 survey ( $n = 163$  patients per intervention arm on average). As a result, the study's power is lower than initially planned but remains adequate for the objectives, summarized as follows:

*Hypothesis 1a.*  $N = 163$  Taper Only participants provide 80% power to confirm that the taper success rate is above 40% at a two-sided significance level of 0.05, when the true success rate is 51.5%.

*Hypothesis 1b.* Comparing the taper success rate between  $n = 140$  Taper Only participants with an initial dose  $< 200$  MEDD and  $n = 23$  Taper Only participants with an initial dose  $\geq 200$  MEDD, the expected 95% confidence interval (CI) for the difference in success rates is [-22%, 22%], assuming a true taper success rate of 50% independent of the initial dose. The width of the CI increases by only 24% due to the sample size reduction.

*Hypothesis 2a.*  $N = 163$  participants per intervention arm provide 80% power for detecting a taper success rate difference of 40% versus 53.5% at a two-sided significance level of 0.05.

*Hypothesis 2b.*  $N = 163$  participants per intervention arm yield an expected 95% CI of [-11%, 11%] for estimating the difference in taper success rates between the Taper + pain-CBT and Taper + CPSMP arms, assuming a taper success rate of 50% in both arms.

*Hypothesis 2c and 2d.*  $N = 163$  participants per intervention arm provide 80% power to detect a between-group difference of 0.311 standard deviation in the 12-month change of continuous outcomes using a two-sample t-test at a two-sided significance level of 0.05.

We also assume an annual drop off rate is less than 19% and we will include all drop outs in our ITT analyses. We will enroll a total of 594 patients to assure the minimum group size requirements for analysis of comparative effectiveness.

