***Access and Intervention Participation.*** The comparison across interventions will be performed according to the intention-to-treat principle. Additional comparisons based on the actual intervention received will be conducted as a sensitivity analysis. We will also study the effect of intervention participation and on treatment outcomes. To this end, we will perform regression analyses to examine the association between the success rate for opioid weaning and other outcomes with session attendance for the pain-CBT and CPSMP arms, separately, while adjusting for identified confounding factors affecting compliance. We will also investigate how baseline factors, such as socioeconomic status, affect the level of compliance.

***Virtual Behavioral Treatment Groups: Comparison of participants who receive in person vs. virtual treatment -*** We will examine mode of delivery as a potential covariate in our analytic models, and study statistician [name] will both advise and implement. Outside of this issue of treatment delivery mode, we must also recognize that COVID itself has introduced a new variable in the study. We will be examining COVID impacts, as well. In regards to the group size and effectiveness of the intervention, the size of the virtual groups are comparable to the size of the in person groups where most groups have an average size of 4 participants. Facilitators stated larger groups (more than 4 participants per cohort) usually provide a more dynamic experience with diverse interactions. While in smaller groups, participants have a chance to go into more detail regarding the skills they are learning and using and any barriers that arise.

***Sensitivity Analysis.*** We will perform sensitivity analyses to account for missing data and non-completion of behavioral interventions. In addition, we will consider an alternative definition of taper success, replacing the 50% reduction in opioid dose with a 30% reduction in opioid dose. A 30% change has been cited as a benchmark for a moderately clinically important difference in the chronic pain literature. Similar analyses will be conducted with this new endpoint as part of the sensitivity analyses.

Statistical analysis will be completed using SAS Enterprise Guide Version 8.3 and R Version 4.1.1.

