## Appendix A. Data Measurement Plan

Name of Measure	Brief Measure Description	Baseline	Weekly (first 6 months)	Monthly*	Months 6, 12
Pain Catastrophizing Scale (PCS) 	13-item scale assesses severity of trait pain catastrophizing tendencies on a 5-point scale (0 = “not at all”; 4 = “all the time”).	x			x
Pain Self-Efficacy Questionnaire (PSEQ) 	2-items measure self-confidence to manage pain and engage in life activities despite pain.	x	x	x	x
NIH PROMIS Measures	Pain intensity (one-item rates average pain intensity during the previous 7 days on a scale of 0 (no pain) to 10 (worst pain imaginable);  depression; and satisfaction with social roles and activities (The National Institutes of Health Patient-Reported Outcomes Measurement Information System short form versions will be used to assess depression and satisfaction social roles and activities. Questions will be framed according to the experience of symptoms or functioning over the past 7 days, and higher scores signify greater severity of these symptoms. Scores will converted from raw scores to t-scores (M = 50 and SD = 10), consistent with their initial publications). 	x	x	x	x
Taper collaboration	Patients rate how much their input was considered by their doctor and overall collaboration in their opioid taper.	x	x	x	x
Alcohol & Substance Use	AUDIT alcohol abuse screen,  DAST illicit drug abuse screen, tobacco use. 	x			x
New Medical Problems or Surgery	New medical issues are assessed, such as dental surgery that might cause a new opioid prescription.	x		x	x
Subjective Opioid Withdrawal Symptom Scale (SOWS)  and correlates	Weekly for the first 6 months questions will assess mood, anxiety, sleep, physical function, pain interference, medication use, discomfort with opioid reduction, and any emergent medical problems.		x	x	x
Beck Depression Inventory  (single suicide risk item)	This question is deployed at baseline and also prompted in the weekly survey (SOWS) when the PROMS depression question is answered with “often” or “always”.	x		x	x
Group Intervention Attendance	Pain-CBT and CPSMP participants will report whether they attended their treatment class in the past week (attendance also recorded by staff).		x**	x**	

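### The within-arm attendance regression is meant to study an effect of participation, but it can be biased by mid-course leaving and early taper difficulty, and the plan specifies neither safeguard

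*Combined protocol and SAP*

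**What the plan says.** The Access and Intervention Participation paragraph puts the main comparison first: "The comparison across interventions will be performed according to the intention-to-treat principle". It then adds a further aim: "We will also study the effect of intervention participation and on treatment outcomes". To serve that aim, "we will perform regression analyses to examine the association between the success rate for opioid weaning and other outcomes with session attendance", for each behavioral arm on its own, "while adjusting for identified confounding factors affecting compliance". The confounders are not listed and not tied to a time point. The next sentence, on predictors of compliance, gives the only example: "We will also investigate how baseline factors, such as socioeconomic status, affect the level of compliance".

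Four other places bear on this:

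- Methodology, Randomization: behavioral treatment should be received "ideally within two to ten weeks of taper initiation".
- Study Arms: pain-CBT has eight weekly sessions and CPSMP has six. The taper description lets patients pause or leave the taper or the study whenever they wish.
- Sample Size Calculations and Study Power: "we will include all drop outs in our ITT analyses". No rule is given for scoring them, and the sentence concerns the ITT analyses only.
- Appendix A: staff record attendance as well as patients. The row for the withdrawal scale (SOWS) reads: "Weekly for the first 6 months questions will assess mood, anxiety, sleep, physical function, pain interference, medication use".

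The Sensitivity Analysis paragraph promises work on missing data and on non-completion of the groups, but names no method.

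**The concern.** Randomization does not protect a comparison of high and low attenders inside one arm. Two routes can link attendance to outcome when the sessions themselves do nothing.

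1. **Leaving during the course.** Someone who leaves at session three cannot attend sessions four to eight. If that person stays in the model and is counted as a failure, one event produces both the low exposure and the bad outcome.
2. **Early taper difficulty.** Withdrawal symptoms, pain or a stalled dose reduction in the first weeks may keep a patient away from the group and also lower the chance of success at month 12. These events come after baseline, so baseline covariates alone cannot remove them.

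Because the stated aim is an effect, a positive slope could be read as showing that more sessions bring more taper success, for either programme.

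**Working it through.** The plan gives no figure for this analysis, so there is none to reproduce.

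**Does attendance overlap the taper?** The recommended pace is 5% of the starting dose per month, with a ceiling of 10% per month. Taking both as shares of the starting dose, a 50% reduction needs 50/10 = 5 months at the ceiling and 50/5 = 10 months at the recommended pace. If groups start 2 to 10 weeks after taper initiation, eight weekly sessions end at about week 10 to 18 and six at about week 8 to 16. Most or all of the course then falls inside the taper.

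**Inputs from the documents.** 594/3 = 198 patients per arm; 8 or 6 sessions; 50% success in both behavioral arms (the Hypothesis 2b power statement); assumed annual loss below 19%. The targets imply 1 − 489/594 = 17.7% loss.

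**Assumptions not in the documents.** Attendance per session of 1/(1 + e^−1) = 73% at average risk; the share leaving during the course; how leavers are scored; and the strength of the link from early taper difficulty to attendance and success.

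**Route 1 by hand, pain-CBT.** A leaver whose last available session is uniform on 0 to 7 is offered 3.5 on average and attends 0.73 × 3.5 = 2.6. A patient who stays attends 0.73 × 8 = 5.8. With leavers scored as failures, success is 0% in the first group and 50% in the second, so a positive slope must appear although sessions do nothing.

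**Null simulation.** 1,500 arms of 198 per scenario; logistic regression of success on sessions attended plus one baseline confounder; true odds ratio (OR) per session 1.00. Cells show estimated OR per session and the share of arms with two-sided p < 0.05.

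| Scenario | 8 sessions | 6 sessions |
|---|---|---|
| Neither route | 1.00, 5% | 1.00, 5% |
| 3% leave in course, scored failures | 1.10, 14% | 1.11, 13% |
| 10% leave, scored failures | 1.27, 74% | 1.30, 66% |
| 19% leave, scored failures | 1.42, 99% | 1.49, 98% |
| 3% or 19% leave at random, excluded | 0.99–1.00, 4% | 1.00, 5–6% |
| Early difficulty, 0.25 log-odds per SD | 1.06, 8% | 1.06, 7% |
| Early difficulty, 0.5 | 1.19, 38% | 1.21, 33% |
| Early difficulty, 1.0 | 1.46, 99% | 1.56, 99% |
| 0.5, plus 10% leave, scored failures | 1.40, 97% | 1.47, 95% |

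The simulation error at a 5% rate is √(0.05 × 0.95/1500) = 0.6 percentage points, so the 4% to 6% entries are consistent with the nominal level. The 19% row puts all assumed loss inside the course and is an upper bound.

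**Second simulation, different assumptions** (600 to 800 arms, total dropout 18%, mean attendance about 70%). For 8 sessions, 3% and 10% leaving gave 9% and 60% false positives; for 6 sessions, 9% and 54%. Excluding those who left before the course ended brought the rate back to about 5%. For early difficulty, odds ratios of 1.35, 1.65 and 2.2 per SD gave 12%, 42% and 93%; adjusting for the early course brought the rate back to about 5%.

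The two agree on both routes. They differ on size (60% against 74% for 10% leaving), so the exact percentages should not be leaned on. Both cover the binary success outcome only. For the continuous outcomes, scoring leavers as failures does not apply, but route 2 does.

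**The case against.** A reader might infer that the plan commits itself to a biased model: dropouts kept and counted as failures, adjustment for baseline factors only, and hence a false dose-response. The documents do not support that.

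- The dropout sentence covers the ITT analyses, and the attendance regression is not one of them. Whether leavers enter it, and how they are scored, is not stated.
- The adjustment clause is not limited to baseline. The baseline sentence describes a separate look at predictors of compliance. Weekly symptom data could be used under the wording as it stands.
- The direction is not given either. Patients with a hard taper might attend more, which would tilt the slope the other way.
- The method sentence already speaks of association, and no numbered hypothesis or primary outcome uses attendance.

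All of this stands, and it makes the bias a risk rather than a demonstrated result. It does not remove the point. The stated aim is an effect, no post-baseline confounder is named, no leaver rule is given, and the promised sensitivity analyses have no method. Adjusting for covariates also does not undo route 1 if leavers are scored as failures.

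A further objection bears on the remedy: pain and withdrawal scores taken after sessions begin may have been changed by those sessions, so adjusting for them could remove real benefit. That is correct, and the fix allows for it.

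**Conclusion.** The point holds as a conditional one. As specified, the attendance regression cannot carry an effect interpretation, and it could show a dose-response when sessions do nothing. The false-positive rate under no effect is about 5% if leavers are excluded at random and early taper difficulty is unrelated to attendance or success. It exceeds 90% under strong versions of either route. Where this trial would fall depends on the early-leaver share, the scoring rule and the strength of the early-taper link, and the documents give none of them. The simulations illustrate a mechanism; they do not measure this trial.

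The between-arm intention-to-treat comparison is unaffected. A reader might also infer that a null ITT result would be explained away as poor compliance; nothing in the plan says so. The change is worth making because it is cheap, not because the main conclusions depend on it.

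**What to change.** In the Access and Intervention Participation paragraph:

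- **Landmark.** Start at the end of the group course, include patients still in follow-up then, and relate month-12 outcome to staff-recorded sessions attended, separately by arm.
- **Covariates.** Name them: baseline MEDD, pain, depression and site, plus taper status recorded before the first session (weekly pain, SOWS, medication use). Leave in-course measures out of a plain regression. If adjustment for them is wanted, weight session by session for the chance of attending, given the weekly data before each session.
- **Wording.** Report an association. Keep the word effect for a randomization-based estimate against Taper Only, such as an instrumental-variable analysis with assignment as the instrument, and state its assumption that assignment acts only through the sessions.

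The cost is SAP text and modest programming on data already collected. Patients who leave before the course ends are excluded, so the interval is slightly wider and the result applies to those still in follow-up. Some weekly covariates may be missing, because the Ethics section makes all survey items optional. Pre-course adjustment is also partial: with a start two weeks into the taper, there is little taper history to adjust for. That is a further reason to report an association only.

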### **Ethics**

As detailed in the Safety Considerations section, ethical considerations include the potential (though unlikely) discomfort when completing surveys. This is addressed by making all survey items optional. For increased withdrawal symptoms, a plan to triage participant needs has been outlined.

### **Informed Consent Forms**

The approved Informed consent form is included below (see Appendix B).

## Appendix A. Data Measurement Plan

Name of Measure	Brief Measure Description	Baseline	Weekly (first 6 months)	Monthly*	Months 6, 12
Pain Catastrophizing Scale (PCS) 	13-item scale assesses severity of trait pain catastrophizing tendencies on a 5-point scale (0 = “not at all”; 4 = “all the time”).	x			x
Pain Self-Efficacy Questionnaire (PSEQ) 	2-items measure self-confidence to manage pain and engage in life activities despite pain.	x	x	x	x
NIH PROMIS Measures	Pain intensity (one-item rates average pain intensity during the previous 7 days on a scale of 0 (no pain) to 10 (worst pain imaginable);  depression; and satisfaction with social roles and activities (The National Institutes of Health Patient-Reported Outcomes Measurement Information System short form versions will be used to assess depression and satisfaction social roles and activities. Questions will be framed according to the experience of symptoms or functioning over the past 7 days, and higher scores signify greater severity of these symptoms. Scores will converted from raw scores to t-scores (M = 50 and SD = 10), consistent with their initial publications). 	x	x	x	x
Taper collaboration	Patients rate how much their input was considered by their doctor and overall collaboration in their opioid taper.	x	x	x	x
Alcohol & Substance Use	AUDIT alcohol abuse screen,  DAST illicit drug abuse screen, tobacco use. 	x			x
New Medical Problems or Surgery	New medical issues are assessed, such as dental surgery that might cause a new opioid prescription.	x		x	x
Subjective Opioid Withdrawal Symptom Scale (SOWS)  and correlates	Weekly for the first 6 months questions will assess mood, anxiety, sleep, physical function, pain interference, medication use, discomfort with opioid reduction, and any emergent medical problems.		x	x	x
Beck Depression Inventory  (single suicide risk item)	This question is deployed at baseline and also prompted in the weekly survey (SOWS) when the PROMS depression question is answered with “often” or “always”.	x		x	x
Group Intervention Attendance	Pain-CBT and CPSMP participants will report whether they attended their treatment class in the past week (attendance also recorded by staff).		x**	x**	
Satisfaction with Group Intervention	Pain-CBT and CPSMP participants will rate their level of satisfaction with their assigned intervention, and separately, with their group instructor on a 7-point rating scale (0 = “not at all satisfied” to 6 = “extremely satisfied”).		x***	x***	
Life Changes survey	Items assess changes to employment, disability status, and/or major life events (new child, loss of a loved one, divorce, major illness, etc.).				x
Study Satisfaction	Patients will rate their level of satisfaction with the study (0 = “not at all satisfied” to 6 = “extremely satisfied”). They may input free text responses and we will monitor these closely.				x
Study Effects	Assesses patient-reported effects (positive and negative) as a result of participating in the study.				x
Patient's Global Impression of Change (PGIC) 	Single item assessing patient's impression of general improvement as a result of participating in the study.				x
COVID-19	Assesses impact of COVID-19 on participants.	x		x	x
Pain Interference	A nine-item Brief Pain Inventory questionnaire measures the level of pain-related interference during the past twenty-four hours across seven domains (such as mood, general activity, etc.) on a scale of 0 (does not interfere) to 10 (completely interferes). Higher scores signify worse pain interference. A total pain interference score will be created by averaging the seven domain scores for each participant. 	x		x	x
Opioid Dose	Participants will self-report their daily prescribed opioid type(s) and dose(s). Daily opioid doses will be converted to a total standardized morphine equivalent daily dose (MEDD) using the 2016 CDC Guidelines for conversion factors including using the escalation of the factor for methadone (i.e. methadone's conversion factor increases at higher doses). 				

\* Monthly questionnaires will be distributed at months 1-5 and 7-11. They will not be distributed at months 6 and 12.

\*\* Group Treatment Attendance Form will only be completed while participant is currently in pain-CBT or CPSMP interventions.

\*\*\* Satisfaction with Group Intervention Form will be distributed following the first and final session of the intervention course only.

